2.6 Community Engagement

Our study population of children in a resource limited setting are vulnerable, and not represented by a patient advocacy group. This study will be embedded within a larger programme of vaccine evaluation and AMR research at MLW, which has been underpinned by longstanding community engagement and involvement (CEI); the NIHR global health research group for vaccines to control respiratory pathogens and AMR (VacAMR) in Malawi. Working with the VacAMR CEI team, we will conduct community engagement activities prior to, during and after study recruitment to engage all key stakeholders, including community leaders, community health workers and hospital clinical staff. This will ensure a clearer understanding of the study within the communities, which will help recruitment and enable meaningful dissemination of study results. Initial community engagement meetings will involve a presentation of the background, purpose and procedures in the proposed study, and an introduction to the study team; the anticipated impact of the study will be highlighted. After study completion, key findings will be shared with participants, communities and local government entities, including key stakeholders through applicable platforms.

2.7 Participant recruitment, enrolment and consent

Healthy children will be recruited from Ndirande community using established random recruitment protocols for pneumococcal carriage surveys [20]. Children with pneumonia in the community will be recruited at time of presentation to Ndirande community healthcare centre and GPCC. Children hospitalised with pneumonia (without admission 6 months prior) will be recruited within 24 hours of admission to QECH. Children rehospitalised with pneumonia within 3 months will be recruited within 24 hours of admission to QECH; health passport screening and carer-reporting will be used to establish prior hospitalisation.

A trained member of the study field team will approach and explain the study to the parent/legally acceptable representative of potential study participants that meet the eligibility

NP Resistome Study

Version 5.0 21/05/2025

Page 16 of 30

criteria in the community setting. Nursing staff at Ndirande community healthcare centre, GPCC and QECH will identify and approach patients eligible for potential study enrolment, for which they will receive a stipend.

[figure not shown]
The parent/legally acceptable representative of each eligible participants will be asked to sign an Informed Consent Form (ICF). Consent will be sought for sample storage, indicating whether the parent/legally acceptable representative authorises storage of NPS and urine samples for 5 years after study completion. In situations where the parent/legally acceptable representative is illiterate, an impartial witness will be present to verify the participant's understanding and will also sign on the ICF; the participant's parent/legally acceptable representative will acknowledge their agreement with a thumbprint. Each participant's parent/legally acceptable representative will be given a copy of the signed ICF, which includes contact information for the principal investigator and the participant identifier.

2.7.1 Withdrawal from study

During the consent process, it will be clearly communicated to the participant's parent/legally acceptable representative that they are free to withdraw from the study at any time. If any participant withdraws before completing the study, we will seek consent from the participant's parent/legally acceptable representative to use already collected data. Participants will not have to provide a reason for withdrawing from the study. All participant's parents/legally acceptable representatives will be informed prior to consent and upon withdrawal that there will be no consequences for their withdrawal from the study at any time.

2.7.2 Participant compensation

Each participant's parents/legally acceptable representatives will receive the equivalent of \$10 (United States Dollars) as travel reimbursement and compensation for time spent on study visits. At the current exchange rate of \$1.00 for MK 1,700, each participant's parents/legally acceptable representatives will be given MWK17,000 for time spent on study activities at each visit in accordance with the guidelines set by COMREC. We will review the currency exchange rates regularly and update the compensation as necessary.

Version 5.0 21/05/2025

Page 17 of 30

2.7.3 Eligibility criteria

Pneumonia will be defined clinically using WHO criteria as the presence of fever, cough, dyspnoea and tachypnoea requiring antibiotic treatment. Current diagnostic guidelines do not recommend chest radiographs for uncomplicated pneumonia.

Patients with HIV infection or severe anaemia (<70g/L) will be excluded; these variables are independently associated with adverse health outcomes. Severe anaemia is the leading cause of recurrent hospitalisation in African children [27]. HIV is associated with post-discharge mortality in childhood pneumonia [28].

2.7.3.1 Inclusion criteria for healthy children in the community

• Child aged between 12-24 months.

2.7.3.2 Exclusion criteria for healthy children in the community

- Presence of any of the following symptoms: fever, cough, difficulty in breathing or fast breathing.
- Currently taking long-term antibiotic prophylaxis, TB treatment or immunosuppressive medications.
- Diagnosis of an immunosuppressive illness, including HIV infection.
- Hospital admission within the past six months.

2.7.3.3 Inclusion criteria for children with pneumonia in the community

- Child aged between 12-24 months.
- Presence of all of the following symptoms: fever, cough, difficulty in breathing and fast breathing.
- Participant has been prescribed antibiotics for treatment of a lower respiratory tract infection on this presentation.

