1.3.2 Primary Objectives

- To measure how the diversity and relative abundance of the nasopharyngeal resistome of children hospitalised with pneumonia differs from the nasopharyngeal resistome of healthy children in the community.
- To measure how the diversity and relative abundance of the nasopharyngeal resistome of children hospitalised with pneumonia differs from the nasopharyngeal resistome of children with pneumonia treated with antibiotics in the community.
- Investigate whether there is measurable persistence of a hospital-acquired nasopharyngeal
 resistome post-discharge, and whether this is associated with adverse health outcomes,
 including recurrent hospitalisation.

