2.0 Methodology

2.1 Study design

This is a multi-site, extended case-control study with a preliminary cohort component to assess the evolution of the NPR under selective pressure of antibiotic use and hospital admission for pneumonia in children aged 12-24 months in Malawi. The study will be led by the PhD student, [name], as a PhD fellowship.

NP Resistome Study

Version 5.0 21/05/2025

Page 10 of 30

In the preliminary cohort component, healthy children in the community will have a NPS collected at the first study visit, to determine the baseline community resistome through metagenomic sequencing (see Figure 1).

To assess the impact of oral antibiotics on the NPR, children presenting with pneumonia to community healthcare clinics, Ndirande and Gateway Primary Care Centre (GPCC), will have a NPS collected at the first study visit and 3-months post-recruitment, to determine the antibiotic-exposed resistome through metagenomic sequencing (see Figure 1).

To understand the impact of broad-spectrum intravenous antibiotics and exposure to a hospital environment on the NPR, children hospitalised with pneumonia (without any hospital admission 6 months prior) to Queen Elizabeth Central Hospital (QECH) will have a NPS collected at the first study visit, discharge and 3-months post-recruitment to determine a hospital-acquired resistome through metagenomic sequencing (see Figure 1).

[figure not shown]

Figure 1. Preliminary cohort component of the study. The yellow diamonds represent the key samples groups for NPR comparison.

The case-control component of the study will examine whether a hospital acquired NPR is associated with adverse health outcomes, specifically re-admission to hospital with pneumonia. Children hospitalised to QECH with pneumonia (without admission 6 months prior), who are not re-admitted within 3 months will form the control group (see Figure 2); these participants will have a NPS will be collected at the first study visit (within 24 hours of admission to hospital), discharge from hospital and 3-months post-recruitment to assess for a hospital-acquired resistome. Those hospitalised within the preceding 6 months will be

NP Resistome Study

Version 5.0 21/05/2025

Page 11 of 30

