Age, gender, co-morbidities, mid-upper arm circumference, pneumococcal vaccination status, antibiotics received 7 days prior to recruitment, haemoglobin level and malaria screening results will be recorded for all participants at recruitment; exposure to tobacco smoke from a household contact and whether the participant was breastfed in their first 3 months of life will also be recorded, as these are independently associated with pneumonia requiring hospitalisation in high-income settings [21]. Mode of childbirth (vaginal versus caesarean section) will also be recorded, as this influences early NPM development, and may be associated with childhood respiratory health [22]. To assess for acquisition of MGEs from the hospital environment, we will record data on duration of hospitalization and incidence of shared bed-spaces for hospitalised study participants, including number of occupants and number of days in a shared bed-space. Shared hospital bed-spaces will be sampled using a swab for metagenomic sequencing. Groups undergoing repeat NPS at 3 months will have health outcomes (including mortality), healthcare interactions (including healthcare facility and hospital attendance/admission) and antibiotic exposure recorded.

Groups being admitted to hospital will have WHO markers of severity in pneumonia recorded, including presence of the following at the time of admission: central cyanosis, oxygen saturations less than 90%, inability to feed, vomiting, convulsions, lethargy and impaired consciousness. To assess for potential influence of healthcare seeking behaviour on hospital re-admission, groups presenting to healthcare clinics and/or hospitals with pneumonia will have the educational level of the parents recorded, and the distance travelled to the healthcare clinic.

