2.7.3.4 Exclusion criteria for children with pneumonia in the community

- Severe anaemia, with a recorded haemoglobin level < 70 grams per Litre.
- Currently taking long-term antibiotic prophylaxis, TB treatment or immunosuppressive medications.
- Diagnosis of an immunosuppressive illness, including HIV infection.
- Hospital admission within the past six months.

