2.7.3.5 Inclusion criteria for children hospitalised with pneumonia

• Child aged between 12-24 months.

NP Resistome Study

Version 5.0 21/05/2025

Page 18 of 30

- Presence of all of the following symptoms: fever, cough, difficulty in breathing and fast breathing.
- Participant has been prescribed antibiotics for treatment of a lower respiratory tract infection on this presentation.

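### The community-pneumonia criteria do not exclude a child referred or admitted to hospital at the index clinic visit, so hospital exposure can enter the comparator's 3-month swab

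*Protocol*

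**What the plan says.** **Intended comparator.** Protocol section 1.3.2 sets the second primary objective as a comparison of hospitalised children with "children with pneumonia treated with antibiotics in the community". Section 2.1 gives the group's purpose: "To assess the impact of oral antibiotics on the NPR, children presenting with pneumonia to community healthcare clinics" have a swab at the first visit and another at 3 months. The hospitalised group is there to show the effect of intravenous treatment and the hospital environment.

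**Eligibility.** Section 2.7.3.3 asks for age 12-24 months, four symptoms, and "Participant has been prescribed antibiotics for treatment of a lower respiratory tract infection on this presentation". Section 2.7.3.4 excludes severe anaemia, certain long-term medications, immunosuppressive illness, and "Hospital admission within the past six months". Sections 2.7.3.5 and 2.7.3.6, for the hospitalised group, contain the same items in the same words, including "Presence of all of the following symptoms: fever, cough, difficulty in breathing and fast breathing".

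**Setting.** Section 2.7 states: "Children with pneumonia in the community will be recruited at time of presentation to Ndirande community healthcare centre and GPCC".

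**Follow-up and analysis.** Section 2.1 has hospital attendances and admissions recorded for groups swabbed again at 3 months. Section 2.9.1 compares study groups with unadjusted t-tests. It summarises a fuller analysis plan that is not at hand.

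**The concern.** The comparator is meant to show what antibiotics do without a hospital stay. Nothing in its written criteria requires management outside hospital. The admission exclusion covers the six months before the visit and not the visit itself, and section 2.7 fixes where a child is recruited but not where the child is then treated.

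A child referred to Queen Elizabeth Central Hospital from the clinic and admitted that day would meet every listed criterion for the community group. At 3 months that child has had the exposure that objective 2 is trying to isolate, yet counts on the unexposed side. The expected effect is to blur the 3-month difference between the groups and so make a real hospital effect harder to see. The same swab also feeds the question of persistence after discharge in the third objective. Clinic nurses screen for eligible patients, so in practice the written list decides who enters.

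**Working it through.** **1. The texts side by side**

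| Item | Community pneumonia (2.7.3.3-2.7.3.4) | Hospitalised pneumonia (2.7.3.5-2.7.3.6) |
|---|---|---|
| Age | 12-24 months | same |
| Symptoms | all four | same |
| Treatment | antibiotic prescribed at this presentation | same |
| Admission | none in the past six months | same |
| Other exclusions | anaemia, medications, immunosuppression | same |
| Outcome of this visit (sent home, referred, admitted) | not mentioned | not mentioned |

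The separation rests on the recruiting site alone. A child who presents directly to the hospital is not taken into the community group. The gap concerns children referred or admitted from the clinic.

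**2. Which samples are affected**

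The first-visit swab is taken when the child presents at the clinic, before any admission that follows, so it is clean. The 3-month swab comes after any such admission and is exposed.

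**3. The plan's own sample size (section 2.5)**

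Inputs: Δ = 0.505 (standardised), two-sided 5%, 90% power.

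n = 2(1.960 + 1.282)² / 0.505² = 82.4, rounded up to 83 per group. This reproduces the stated figure. Power at 83 per group is Φ(0.505/√(2/83) − 1.96) = 90.2%.

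**4. Illustration of dilution at 3 months**

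Let c be the share of the 83 evaluable community children who have been in hospital before the 3-month swab. The protocol gives no value, so c is an assumption. If those children look on average exactly like the hospital group, the expected difference becomes 0.505(1 − c), and power is Φ(0.505(1 − c)/√(2/83) − 1.96).

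| c (assumed) | Children of 83 | Expected difference | Power |
|---|---|---|---|
| 0 | 0 | 0.505 | 90.2% |
| 2% | about 2 | 0.495 | 89.0% |
| 5% | about 4 | 0.480 | 87.1% |
| 10% | about 8 | 0.455 | 83.4% |
| 20% | about 17 | 0.404 | 74.0% |

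The small extra variance from mixing two kinds of children is ignored: at c = 10% it is 0.10 × 0.90 × 0.505² = 0.023 on a variance of 1.

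**5. Power if such children are left out and not replaced**

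Power is Φ(0.505/√(1/83 + 1/(83(1 − c))) − 1.96): 89.5% at c = 5%, 88.6% at 10% and 86.6% at 20%. An analysis without them gives up little power.

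**The case against.** **The group is defined by its setting.** The heading, objective 2 and the stated purpose all say community, so a referred child plainly does not belong. That shows the intent, and it is why one line suffices. It does not put the condition on the list that staff apply.

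**Admissions during follow-up can be left to the analysis plan.** This stands. The protocol records those admissions, and its silence does not establish that an admitted child will be analysed as a community child. It does not answer the index visit, which is a question of eligibility and so belongs in the protocol.

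**The size is speculative.** This also stands. No value of c comes from the protocol. Full dilution is a strong assumption, since section 2.4 chose 3 months so that the resistome could recover. The figures showing which samples are compared are not available, so it cannot be confirmed which pair carries the main test.

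**Stronger readings that the protocol does not support:**

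- *One child could be enrolled in both groups, breaking the independence of the t-test.* Section 2.4 has community participants recruited before hospital participants, and the later return visits are for healthy children. Overlap is possible near the change of phase or on a later admission, but it is marginal.
- *Hospital children are purged of re-admissions while community children are not.* The rule that children "who are not re-admitted within 3 months will form the control group" belongs to the case-control component, where re-admission is the outcome. For the cohort comparison, section 2.1 states no exclusion after enrolment in either group, so there is no rule to mirror.
- *Severity must be recorded for community children.* Section 2.1 says "Groups being admitted to hospital will have WHO markers of severity in pneumonia recorded", and section 2.9.2 uses severity in the re-hospitalisation model. Extending the record to clinic children may be useful, but its absence is not an error on this point.

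**Conclusion.** The point holds as a gap in eligibility. The community list admits a child who is referred or admitted at the index visit, which conflicts with the comparator named in objective 2 and with the oral-antibiotic purpose in section 2.1. The consequence is confined to the 3-month swab and to what is built on it, and the likely direction is toward no difference.

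The size is unknown. Under the two assumptions above (a chosen admission share and full resemblance to the hospital group), power falls from 90% to 87% at 5% and to 83% at 10%. The 74% at an assumed 20% should not be read as a forecast. The sample size calculation itself is correct.

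A reader might infer that the whole hospital-versus-community comparison is compromised. The documents do not support that: the first-visit comparison is untouched, and the handling of later admissions may be settled in the analysis plan. This is a cheap improvement, not a fundamental flaw.

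**What to change.** 1. In section 2.7.3.4, add the exclusion: *Child referred or admitted to hospital at this presentation.* Including referral lets staff apply it at the visit. The list already depends on the prescribing decision, so the decision to refer should usually be known by then.

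2. For community children admitted after enrolment but before the 3-month swab, keep them in the main comparison and add a sensitivity analysis without them, using the admissions already recorded under section 2.1. Removing them from the main comparison would select on an event after enrolment and leave the milder children in the comparator. This can be stated in section 2.9.1 or in the analysis plan.

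The cost is one eligibility line, slightly fewer eligible clinic children and one extra analysis. No new data are needed for the sensitivity analysis.

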2.7.3.4 Exclusion criteria for children with pneumonia in the community

- Severe anaemia, with a recorded haemoglobin level < 70 grams per Litre.
- Currently taking long-term antibiotic prophylaxis, TB treatment or immunosuppressive medications.
- Diagnosis of an immunosuppressive illness, including HIV infection.
- Hospital admission within the past six months.

2.7.3.5 Inclusion criteria for children hospitalised with pneumonia

• Child aged between 12-24 months.

NP Resistome Study

Version 5.0 21/05/2025

Page 18 of 30

- Presence of all of the following symptoms: fever, cough, difficulty in breathing and fast breathing.
- Participant has been prescribed antibiotics for treatment of a lower respiratory tract infection on this presentation.

2.7.3.6 Exclusion criteria for children hospitalised with pneumonia

- Severe anaemia, with a recorded haemoglobin level < 70 grams per Litre.
- Currently taking long-term antibiotic prophylaxis, TB treatment or immunosuppressive medications.
- Diagnosis of an immunosuppressive illness, including HIV infection.
- Hospital admission within the past six months.

2.7.3.7 Inclusion criteria for children re-hospitalised with pneumonia

- Child aged between 12-24 months.
- Presence of all of the following symptoms: fever, cough, difficulty in breathing and fast breathing.
- Participant has been prescribed antibiotics for treatment of a lower respiratory tract infection on this presentation.
- Hospital admission to ANY hospital with a lower respiratory tract infection within the past 3 months.

2.7.3.8 Exclusion criteria for children re-hospitalised with pneumonia

- Severe anaemia, with a recorded haemoglobin level < 70 grams per Litre.
- Currently taking long-term antibiotic prophylaxis, TB treatment or immunosuppressive medications.
- Diagnosis of an immunosuppressive illness, including HIV infection.

2.8 Safety

Participants' safety will be prioritised throughout the study. All potential, foreseeable safety risks will be fully outlined and disclosed verbally during the consent process, and in writing on the participant information sheet and ICF. The process of NPS collection can cause slight discomfort and irritation for children; in rare instances (with certain underlying conditions) the child may experience light bleeding after sample collection. Staff collecting NPS will be trained to minimise discomfort, and provide participant and parent/legally acceptable representative reassurance during the sample collection process.

NP Resistome Study

Version 5.0 21/05/2025

Page 19 of 30

2.9 Statistical analysis

The statistical analysis plan is briefly summarised below. A detailed statistical analysis plan will be developed prior to starting recruitment.

2.9.1 Primary analysis

Participants will be gender-matched across groups. To establish differences in NPR composition the mean NPR diversity in a sample (measured using the Shannon index), mean relative abundance of all ARGs in a sample and mean relative abundance of specific ARGs in a sample will be compared between study groups using unadjusted t-tests, as summarised in Figure 4. Statistical analysis will be performed in R. Results will be presented in tables and illustrative heatmaps.

[figure not shown]

Figure 4. Plan for statistical analysis of NPR composition.

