2.5 Sample size and calculations

There is no established method for sample size calculation in resistome studies; we use an approach for microbiome studies [25]. Differences in gut plasmidome composition have been detected with 41 participants per group [26], but NPR has a lower biomass than gut resistome, therefore the resistome is likely to be less diverse, with a lower relative abundance of ARGs. NPR analysis 3.5 years post-antibiotic exposure in a cluster-randomised trial of mass-azithromycin administration shows a trend toward decreased NPR diversity (p = 0.07) in azithromycin clusters when compared to placebo clusters, with just 25 samples per group (unpublished data).

We have used the measured difference in relative abundance of a specific macrolide ARG (ermX) 3.5 years after mass-azithromycin administration (unpublished data) as a medium effect size that maybe clinically relevant (Δ = 0.505). Using the approach for microbiome studies, accepting 90% power and 5% type I error (95% confidence interval),

NP Resistome Study

Version 5.0 21/05/2025

Page 15 of 30

we've calculated that we will require a sample size of 83 participants in each group to detect this effect size, using the formula $n=2(Z_{1-\alpha/2}+Z_{1-\beta})^2/\Delta^2$ [25].

In total we aim to recruit 350 study participants: 83 healthy community participants, 92 participants with pneumonia in the community, 92 participants admitted to hospital with pneumonia and 83 participants re-admitted to hospital with pneumonia. Study groups with a sample size of 92 participants permit a 10% loss to follow up.

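### The 83 per group is sized for one comparison of one measure at 5%, but the primary analysis is an unranked, open-ended set of t-tests with no error control stated

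*Protocol*

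**What the plan says.** **Sample size (Protocol, 2.5).** The error rates are given once: "accepting 90% power and 5% type I error". The effect is the "measured difference in relative abundance of a specific macrolide ARG (ermX) 3.5 years after mass-azithromycin administration", treated as a "medium effect size that maybe clinically relevant (Δ = 0.505"). The result is that "we will require a sample size of 83 participants in each group to detect this effect size". The formula is the usual normal one for two means, two-sided, with nothing in it for more than one test.

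**Primary objectives (Protocol, 1.3.2).** There are three. The first two share the stem "To measure how the diversity and relative abundance of the nasopharyngeal resistome of children hospitalised with pneumonia differs", once against healthy children and once against children with pneumonia treated in the community. Each therefore covers both diversity and abundance. The third concerns persistence after discharge and its link to adverse outcomes.

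**Primary analysis (Protocol, 2.9.1).** The groups are compared by unadjusted t-tests on the mean Shannon index and on two kinds of abundance: "mean relative abundance of all ARGs in a sample and mean relative abundance of specific ARGs in a sample will be compared". The text does not say which measure leads, how many specific ARGs are tested or which ones, or how error is shared among the tests. The section refers to Figure 4 for a summary, and that figure is not reproduced in the copy reviewed. Section 2.9 says a detailed SAP will be written before recruitment.

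**The concern.** Sections 2.5 and 2.9.1 describe different analyses. A reader of 2.5 would take it that the study has a 5% chance of a false primary claim and a 90% chance of finding the planned effect. Under 2.9.1 there are at least six primary tests (three measures by two contrasts, counting only one specific ARG), and the specific-ARG part has no upper limit. A difference in any one of them could be reported as a primary result.

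The consequence for power is separate. The sample size has no allowance for multiplicity, so any correction added later in the SAP takes power from the 90% already promised. An SAP can add a correction; it cannot add participants.

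**Working it through.** **1. Reproduce the plan's figure.** Inputs from 2.5: two-sided α = 0.05, power 0.90, Δ = 0.505. The formula treats Δ as a standardised difference, so an SD of 1 is implied.

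n = 2(1.960 + 1.2816)² / 0.505² = 82.4, rounded up to 83. The stated figure reproduces. At n = 83 the power is Φ(0.505·√(83/2) − 1.960) = Φ(3.253 − 1.960) = 90.2%, or 89.9% with the noncentral t. Both figures hold for one test.

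**2. Count the tests the text supports.** The first two objectives give two contrasts: hospitalised against healthy, and hospitalised against community pneumonia. Section 2.9.1 gives three kinds of measure. Counting one specific ARG, that is 3 × 2 = 6 tests.

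**3. Study-wide false-positive rate with each test at 5%.** If all six were independent it would be 1 − 0.95⁶ = 26.5%. They are not independent: both contrasts use the same hospitalised group, and the measures are correlated to an unknown degree. Simulating three groups of 83 with no true difference:

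| Measures tested | Correlation 0 | Correlation 0.7 |
|---|---|---|
| 3 (Shannon, total, one ARG) | 25% | 19% |
| 22 (two summary measures + 20 ARGs) | about 88% | about 47% |

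The 20 ARGs are an assumption; the protocol gives no number. The row shows direction and scale only.

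**4. Power at 83 per group if error is controlled.** Power = Φ(3.253 − z), with z the two-sided critical value (normal approximation):

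| Level per test | z | Power at n = 83 | n per group for 90% |
|---|---|---|---|
| 0.05 | 1.960 | 90.2% | 83 |
| 0.05/2 | 2.241 | 84.4% | 98 |
| 0.05/3 | 2.394 | 80.5% | 106 |
| 0.05/6 | 2.638 | 73.1% | 121 |

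Under Holm across two contrasts, a given contrast is tested at 0.05/2 or, if the other is already significant, at 0.05. Its power therefore lies between 84.4% and 90.2%.

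**5. Does the t-test itself fail on skewed data?** Simulated at 83 per group with both groups sharing one assumed distribution, the type I error is 2.8–5.0% for lognormal data (log-SD 2 down to 0.5) and 2.0–3.4% with 90% down to 30% zeros. Power for a raw-scale shift of 0.505 SD is 89–95%. Type I error exceeds 5% only when the means are equal but the shapes differ (8.4% for log-SD 1 against 1.5; 19.6% for 1 against 2).

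**6. Scale of analysis.** If the effect is multiplicative, with a shift of 0.505 SD on the log scale, a raw-scale t-test has power of about 72%, 54% and 36% at log-SD 1, 1.5 and 2, against about 90% for a t-test on logs. The log-SDs are assumed.

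**The case against.** **The SAP may settle it.** Multiplicity methods, transformations and zero handling are ordinary SAP content, and 2.9 calls itself a summary. This stands for the detail. It does not cover the mismatch that the protocol itself fixes: a sample size for one test beside a primary analysis of many.

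**Figure 4 may rank the measures.** It is not shown, so the claim can only be that the text ranks none.

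**The word unadjusted may mean only without covariates,** in contrast to the regression in 2.9.2. That is possible. On either reading no error control is stated.

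**A reader might infer a nine-test primary family,** adding re-admitted against hospitalised children as a third contrast, for a false-positive rate of 26–33%. The text does not support this. The association with re-hospitalisation is tested by conditional logistic regression under the secondary analyses, so a primary t-test for it would be an inference.

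**A reader might infer that both error rates in 2.5 fail because abundances are skewed.** They do not. Step 5 shows that at 83 per group the per-test error stays near or below 5% under a common skewed shape, and power holds for a 0.505 SD shift on the analysed scale. The lower powers in step 6 arise largely because a 0.505 SD shift on the log scale is only about 0.37, 0.23 and 0.12 SD on the raw scale. Section 2.5 does not say that Δ is on a log scale.

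**A reader might take total ARG abundance to be what Δ was based on.** It is not. Δ comes from one gene, so using it for any summary measure is an assumption.

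**Separate objectives in an observational study need no joint control.** This is a defensible view across objectives. It is weaker within one objective, where several unranked measures answer the same question.

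**Conclusion.** The point holds in a limited form. The 5% and 90% in 2.5 are correct for one two-group comparison of one measure. They do not describe the primary analysis in 2.9.1, where the study-wide false-positive rate is about 19–25% for the six tests the text supports, and higher with each further ARG.

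This rests on each test being run at 5% (the only level the protocol gives), on one specific ARG as the minimum, and on correlations between measures of 0 to 0.7. The 47–88% range depends further on the assumed 20 genes. The power figures need no assumption beyond the protocol's own Δ and n.

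The log-scale point is an improvement worth making, not evidence that the stated power is wrong.

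**What to change.** **In 2.9.1**
- Name one lead primary measure for the two between-group objectives and control error across those two contrasts, for example by Holm at 5%.
- Make the other summary measure secondary.
- Report specific ARGs under a 5% Benjamini–Hochberg false discovery rate, taken over all ARGs and contrasts tested.
- Say what unadjusted means.
- Analyse relative abundance on a log scale with a stated rule for zeros.

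**In 2.5**
- State that 90% applies to one comparison at 5%, and that power at 83 per group is about 84% at 0.05/2 (80% at 0.05/3).
- State that Δ is a standardised difference drawn from a single ARG and is assumed to carry over to the lead measure.

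**Cost.** Wording in the protocol and SAP, with no change to recruitment. The stated power falls from 90% to about 84% for each lead contrast at the stricter Holm step; keeping 90% there would need 98 per group instead of 83. Results on a log scale are ratios, which are less direct to interpret than differences in mean abundance.
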